## 7 TESTS AND EVALUATIONS

[figure not shown]
All required observations with their schedules are summarized in [Appendix D, Table 1](#) (Part 2 and 3) and [Appendix D, Table 2](#) (Part 4). Unless otherwise stated, the assessments below pertain to patients enrolled in both Part 3 and Part 4 of the study. Concomitant medications will be recorded from the time of informed consent through the safety follow-up visit. AEs will be recorded from the start of the first dose of study treatment through the safety follow-up visit (see [Section 9.4](#)).

Routine laboratory assessments, such as serum chemistries, hematology, coagulation and urinalysis, will be performed locally. In order to minimize required blood volume, pediatric tubes are suggested (but not required) for hematology and serum chemistries.

Special tests such as PK, ADA, and pharmacodynamic/biomarker samples will be performed centrally or as individually indicated. Additional information on the handling and processing of these samples may be found in the separate Laboratory Manual.

For subjects enrolled in the phase 1b expansion part of the study parts 2-4, there is a window of  $\pm$  2 days (2 days early or 2 days later) for any scheduled treatment days to permit holidays, travel, clinic scheduling and other delays from Week 2 and beyond. If the actual visit occurs greater than 2 days from the planned visit, that planned visit will be considered to have been missed and subjects should proceed with the next planned visit. All response assessments have an allowable window of  $\pm$  1 week. Fresh biopsies, photographs and TCR V $\beta$  whole blood collections also have a  $\pm$  1 week allowable window to align with response assessments.

CCI

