## 7.12 Safety Follow-up Visit

Approximately 30 days after the final dose of TTI-621 ( $\pm$  2 days), the following will be performed. If treatment-emergent abnormalities are present at the end-of-treatment visit, repeat pertinent labs or studies:

- symptom driven physical examination and ECOG score
- body weight
- vital signs
- serum chemistries
- hematology
- TSH (only for subjects in the nivolumab combination cohort)
- serum for ADA analysis; subjects who are seropositive at safety follow-up, should be monitored at least quarterly for 1 year post study to assess persistence of antibodies
- status of unresolved AEs

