## 7.13 Long-term Follow-up (Expansion Phase Only)

For a period of 1 year following the safety follow-up visit, subjects treated in the expansion phase will be contacted at least quarterly ( $\pm 1$  week) via routine clinic visit and/or telephone call to assess the following:

- subsequent anticancer therapies
- status of any ongoing/chronic AEs that were treatment-emergent
- persistence of ADA in those subjects who seroconverted
- date of disease progression (if not documented on study)
- survival status

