#### 8.4.6 Efficacy Analyses

Efficacy analyses will be conducted using the Full Analysis Set and, where appropriate, the Per-protocol Set; in addition, the overall response rate will also be presented for the Response-Evaluable Set.

The overall response rate will be estimated for each cohort using disease-specific response criteria (see [Section 7.14.1](#)). The duration of response (DOR) will be calculated for a subject who achieves a response, and is defined as the number of weeks from the start date of the response (and subsequently confirmed) to the first date recurrent or progressive disease is documented. If a subject dies, irrespective of cause, without documentation of recurrent or progressive disease beforehand, then the date of death will be used to denote the response end date.

Progression-free survival (PFS) is defined as the number of weeks from the date of the first dose of study drug to the earliest of documented recurrent or progressive disease or death due to any cause without prior progression. Leukemia-free survival (LFS) will be calculated in the same manner, as appropriate.

DOR and PFS will be summarized descriptively using the Kaplan-Meier method with 95% CI calculated using Greenwood's formula. Median follow-up for each endpoint will be estimated according to the Kaplan-Meier estimate of potential follow-up. The PFS rate at selected landmarks (e.g., 6 months) and corresponding 95% CIs will be estimated using the Kaplan-Meier method. Greenwood's formula will be used to calculate the standard errors of the Kaplan-Meier estimate and upper and lower limits of the 95% CI.

For DOR and PFS, subjects who meet one or more of the following conditions will be right-censored as follows:

- subjects with no baseline or postbaseline disease assessments unless death occurred prior to the first planned assessment (in which case the death will be considered a PFS event)
- subjects who initiate subsequent anticancer therapy in the absence of documented progression
- subjects who die or have disease progression after missing 2 or more consecutively scheduled disease assessment visits
- subjects who are last known to be alive and progression-free on or before the data cut-off date

For such subjects, the progression or censoring date will be determined based on described conventions (Food and Drug Administration, 2007), as outlined in the SAP.

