**Appendix D. Table 2. Phase 1b - Part 4 Dose Optimization: Schedule of Assessments**

Assessments	$\leq$ -D14	W1 a	W2 D1	W3 D1	W4 D1	W5 D1	W6 D1	W7 D1	W8 D1	W9 + D1	EOT	SFU c	LTFU
	DLT evaluation Period												
	Except where otherwise noted these visit pre-dose assessments can be performed up to 24 hours pre-infusion (see also Section 7). All scheduled treatment days have a window of $\pm$ 2 days											$\leq 1$ Wk h	$\pm 2$ D
Informed consent (within 30 days)	X												
Medical, malignancy history	X												
Physical exam b , ECOG	X	pre m	pre m	pre m	pre m	pre m	pre m	pre m	pre m	pre m	X	X m	
Body weight	X	pre	pre	pre	pre	pre	pre	pre	pre	pre Wk 10 + Q2 wks l	X	X	
Vital signs c	X	pre, (1 hr [EOI]), 2 hr, 4 hr	pre	X	X								
Disease assessment (incl. photographs) d	X i								post	post Wk16, 24 +Q12 wks k	X g		
12-lead ECG	X	pre and post j			pre				pre	pre Wk12 + Q4 weeks	X		
QOL by FACT-G, SKINDEX29	X								post	post Wk16, 24 +Q12 wks k	X		
TTI-621 infusion s		X	X	X	X	X	X	X	X	X			
AEs		X	X	X	X	X	X	X	X	X	X	X	X (TEAE)
Prior/concomitant medications	X	X	X	X	X	X	X	X	X	X	X		
Survival Status													X
Subsequent anticancer therapies													X

D = Day; Post = after start of TTI-621 infusion, EOT = end of treatment visit; SFU = safety follow-up visit; LTFU = long term safety follow-up visit; EOI = end of infusion (1 hr)

Assessments	≤ -D14	W1 a	W2 D1	W3 D1	W4 D1	W5 D1	W6 D1	W7 D1	W8 D1	W9 + D1	EOT	SFU c	LTFU	
DLT Evaluation Period														
		Except where otherwise noted the visit pre-dose assessments can be performed up to 24 hours pre-infusion (see also Section 7 ). All scheduled treatment days have a window of ± 2 days										≤1 Wk h	± 2D	Q4 (±1 wk)
Local Laboratory Assessments														
Hepatitis B/C panel	X													
Pregnancy test (women of childbearing potential)	X (serum)				pre (serum or urine)				pre (serum or urine)	pre Wk 12 then Q4 wks (serum or urine)				
Hematology n	X	pre, 1 hr, (EOI), 2 hr, 4 hr D2, D4	pre, 4 hr, (D2 n* if clinically indicated)	pre, 4 hr, (D2 n* if clinically indicated)	pre	pre	pre	pre	pre	pre	X	X		

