### **3.5.4 Prior and Subsequent Systemic Therapies**

Systemic therapy regimens are collected on two CRFs:

- Prior Systemic Therapy
- Subsequent Systemic Therapy

Medications collected on both CRFs will be coded by Pfizer to preferred terms by means of the World Health Organization Drug Dictionary (WHODRUG).

Subjects reporting multiple medications within the same PT will be counted only once for that PT on medication summaries. PTs in summaries will be displayed in order of decreasing total frequency of occurrence.

Prior Systemic Therapies will be summarized by PT and by:

- Initial assigned dose levels or initial assigned dosing schedules (in the case of Part 4 biweekly) for Part 1 and Part 4 (Dose Escalation cohorts)

- Monotherapy or combination therapy for Part 2 and Part 3
- Indication within monotherapy and by combination therapy for Part 2 and Part 3

In addition, a listing will be provided that contains the verbatim medication term, PT, therapy start and end dates, study drug start date, duration of therapy, route of administration, best overall response, and the reason the therapy ended.

Subsequent Systemic Therapies will be summarized by PT. In addition, a listing will be provided. This listing will contain the verbatim medication term, PT, therapy start date, and the study day on which the therapy started.

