### **3.7.2 Duration of Response and Progression Free Survival Time**

The time-to-event endpoints measured in this study are defined in terms of the following dates.

- Date of first dose = Date of first dose as recorded on Treatment CRF
- Date of response = Earliest of the consecutive dates at which subject is assessed in a responder category
- Date of last non-PD assessment = Date of last non-missing assessment other than NE, NA, or Unknown
- Date of progression = Date at which subject is first assessed as having progressive disease
- Date of initiation of anticancer treatment = Earliest concomitant medication start date for concomitant medications identified by sponsor as being anticancer treatments

- Date of death = Date of death from any cause as recorded on Death Page CRF

The following time-to-event endpoints will be calculated for each subject.

- DOR for subjects who achieved an objective response = Duration of response (in weeks) =  $[\min(\text{Date of progression}) - \text{Date of response} + 1]/7$
- PFS = Progression free survival time (in weeks) =  $[\min(\text{Date of progression}, \text{Date of death}) - \text{Date of first dose} + 1]/7$

In the case of missing dates (ie, subjects without an event), the following censoring rules will be applied.

Endpoint	Censor if:	Censoring date = Minimum of indicated dates		
		Date of last non-PD assessment	Date of initiation of anticancer treatment	Date of death
DOR	Death prior to progression			X
DOR or PFS	Subsequent anticancer therapy is initiated in the absence of documented progression		X	
	Death or progression after $\geq 2$ assessments of NE, NA, Unknown, or Missing	X		
	Alive & progression free	X	X	

DOR and PFS will be displayed in listings.

The number of subjects with event for DOR and PFS will be summarized. Median time to event, the 25th and 75th percentiles of time to event, along with 95% CI for DOR and PFS will be estimated according to the Kaplan-Meier estimate using the Brookmeyer-Crowley method.

Additionally, the PFS rate at selected landmarks (e.g., 6 months) and corresponding 95% CIs will be estimated using the Kaplan-Meier method. Greenwood's formula will be used to calculate the standard errors of the Kaplan-Meier estimate and upper and lower limits of the 95% CI.

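### SAP 3.7.2 dates new anticancer therapy from concomitant medications alone, so therapy begun after the safety follow-up visit cannot trigger the protocol's PFS and DOR censoring rule

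*SAP*

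**What the plan says.** **The rule.** Protocol 8.4.6 lists, among those to be right-censored for DOR and PFS, "subjects who initiate subsequent anticancer therapy in the absence of documented progression". It leaves the dating conventions to the SAP.

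**The date.** SAP 3.7.2 repeats the rule in its censoring table and defines the date that feeds it: "Date of initiation of anticancer treatment = Earliest concomitant medication start date for concomitant medications identified by sponsor as being anticancer treatments". The sentence introducing the table confines the censoring rules to those with no event on record.

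**How long that source runs.** Protocol Section 7: "Concomitant medications will be recorded from the time of informed consent through the safety follow-up visit". Protocol 7.12 places that visit "Approximately 30 days after the final dose of TTI-621". The list of procedures in 7.12 does not mention concomitant medications. In Appendix D Tables 1 and 2 the row "Prior/concomitant medications" appears to have its last mark at the end-of-treatment visit.

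**Where later therapy is recorded.** SAP 3.5.4: "Systemic therapy regimens are collected on two CRFs". One covers prior therapy and the other subsequent therapy, and the listing of subsequent therapy carries a start date. Protocol 7.13 adds: "For a period of 1 year following the safety follow-up visit, subjects treated in the expansion phase will be contacted at least quarterly". Those contacts collect subsequent anticancer therapies, progression dates not already captured, and survival status.

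**The concern.** The rule and its data source do not match. The therapy the rule is aimed at will often begin after treatment has stopped, and Protocol 6.8.3 prohibits other systemic anticancer treatment before then. The source closes about a month after the last dose, while progression and survival are collected for a further year. An event can therefore be recorded after a change of therapy that the derivation cannot see, and it would be counted as an event on TTI-621.

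PFS and DOR are secondary endpoints in Parts 2 and 3, and DOR is also one in Part 4. The protocol's design text says durability of response may influence the sponsor's decision on Stage 2 of the Part 3 cohorts.

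**Working it through.** The plan states no event count, power or expected value for PFS or DOR, so there is no figure to reproduce. The check has four steps.

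**1. Reach of the source after last dose**
- Safety follow-up: about 30 days (Protocol 7.12). Long-term follow-up: 1 year (Protocol 7.13). Total: 30 + 365 = 395 days.
- Concomitant medications under Protocol Section 7: 30/395 = 7.6% of that time.
- Concomitant medications if recording stops at end of treatment (within 1 week, as the schedule tables suggest): 7/395 = 1.8%.
- These are shares of time. The documents do not say how many subjects start new therapy inside or outside the window.

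**2. What happens when therapy starts after safety follow-up, without progression**

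| Later course | SAP 3.7.2 as written | Effect |
|---|---|---|
| No later event | Censored at last non-PD assessment | Nothing extended |
| Progression or death after 2 or more missing or non-evaluable assessments | Censored at last non-PD assessment | Nothing extended |
| Progression or death with fewer than 2 such assessments | PFS event at the later date | Departs from Protocol 8.4.6 |
| Responder dies without progression, fewer than 2 such assessments | DOR censored at death | Departs from 8.4.6; later than the new therapy |

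The third row can occur under the actual schedule, because assessments are 12 weeks apart after Week 24. Take a subject assessed progression-free at Week 24 who stops then. Safety follow-up falls near Week 28, new therapy starts at Week 30, and death occurs at Week 40. Only the Week 36 assessment is missed, so the missed-assessment rule is not met. The SAP counts a PFS event at Week 40. With the therapy date available, the same SAP table would censor at Week 30.

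**3. Direction for PFS (illustration; every input is assumed)**

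Times are exponential with median PFS on TTI-621 of 16 weeks, so h = ln 2/16 = 0.0433 per week. A share f starts new therapy before an event, at rate h·f/(1−f). The hazard after the start is HR × h. There are 400,000 simulated subjects. No start is captured and every later event is counted. The missed-assessment rule is not applied, so these shifts tend to be large.

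Kaplan-Meier median PFS in weeks:

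| f | Censored at new therapy | HR 0.33 | HR 0.5 | HR 1.0 | HR 1.5 | HR 2.0 |
|---|---|---|---|---|---|---|
| 10% | 15.9–16.0 | 16.5 | 16.4 | 16.0 | 15.8 | 15.5 |
| 20% | 16.0 | 17.1 | 16.8 | 16.0 | 15.4 | 15.0 |
| 30% | 15.9–16.1 | 18.0 | 17.4 | 16.0 | 15.2 | 14.5 |

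- 26-week PFS at f = 20% is 0.364 (HR 0.33) to 0.291 (HR 2.0), against 0.323–0.325 with censoring at new therapy.
- Capturing half of the starts roughly halves the shift. At f = 20% the median is 16.6 weeks for HR 0.33 and 15.5 for HR 2.0.
- If instead every subject who switches is censored at a last assessment on an assumed 8-week grid, the median falls to 15.7, 15.3–15.4 and 14.8–15.0 weeks for f = 10%, 20% and 30%.

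**4. Direction for DOR when a responder dies without progression**

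The Kaplan-Meier curve is the product of (1 − d/n) over event times, with d events among n at risk. Censoring at death instead of at new therapy adds one subject to n at each event time in between and leaves d unchanged. Since 1 − d/(n+1) ≥ 1 − d/n, the curve cannot fall. For example, with d = 1 the factor goes from 1 − 1/5 = 0.80 to 1 − 1/6 = 0.83.

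**The case against.** The strongest reply is that the rest of the SAP table already does much of the work. Event-free subjects are censored at the last non-PD assessment, normally before the new therapy. Progression or death after two or more missing assessments goes back to the same date. Therapy started between last dose and safety follow-up can still be captured. PFS and DOR are descriptive, with no hypothesis test, and the primary endpoint is adverse events. The formal Stage 2 criterion is a count of responders. All of this stands and it limits the point, but none of it supplies the missing therapy date for the cases in the last two rows of the table in step 2.

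Four stronger readings are tempting, and the documents do not support them:

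- **That later therapy extends PFS and DOR.** For PFS this requires the next therapy to lower the hazard; step 3 shows the opposite is possible. A subject who stops at Week 8, switches at Week 14 and progresses at Week 40 does not prove it. With no assessments after Week 8, Weeks 16, 24 and 36 are missed and the missed-assessment rule would apply, if off-treatment visits count as missing. The SAP does not say whether they do.
- **That the rule mostly cannot fire.** This is shown for follow-up time only.
- **That every late progression becomes an event.** SAP 3.7.1 takes progression from response-assessment categories. Whether a date reported by telephone in long-term follow-up feeds that derivation is not stated. Death does feed PFS.
- **That palliative radiotherapy should trigger the rule.** Protocol 6.8.2 allows it within limits for symptom relief while TTI-621 continues, and 8.4.6 does not class it as subsequent anticancer therapy.

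On the lead-in, it is fair to say that the table itself censors some recorded deaths and progressions, so the sentence can hardly be meant literally. As written, though, it would let a later event override even a captured therapy start.

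**Conclusion.** The point holds as a mismatch between rule and data source. Therapy started after safety follow-up cannot trigger the Protocol 8.4.6 censoring rule, and the lead-in to the SAP table leaves unclear whether a captured start would do so once a later event exists. PFS can be biased in either direction. For a responder who starts unseen therapy and then dies without progression, outside the missed-assessment rule, DOR is lengthened or unchanged.

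The size cannot be determined from the documents. They do not give the number of subjects switching before progression, the timing of the switch or the hazard afterwards. Under the assumptions in step 3 the median PFS of 16 weeks becomes 14.5 to 18.0 weeks at the extremes, with none of the starts captured.

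The conclusion assumes that later therapies are entered on the Subsequent Systemic Therapy CRF and not also as concomitant medications; the CRF itself is not among the documents. These are descriptive secondary endpoints, so this is a correction worth making but does not threaten the study's primary conclusions.

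**What to change.** In SAP 3.7.2:

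1. Define the date of initiation of anticancer treatment as the earliest start after first dose across (a) the Subsequent Systemic Therapy CRF, (b) the long-term follow-up record of subsequent anticancer therapies, and (c) concomitant medications that the sponsor flags as anticancer.
2. Replace the lead-in to the censoring table. It should say that a subject who starts subsequent anticancer therapy before documented progression is censored even if a later progression or death is recorded.

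Palliative radiotherapy should not be added automatically, because the protocol does not call for it. While the table is open, two clarifications would help: whether scheduled assessments after treatment stops count as missing, and whether recording of concomitant medications ends at safety follow-up (Protocol Section 7) or at end of treatment (Appendix D).

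The cost is some SAP wording and one derived date, built from data already collected. PFS and DOR will carry slightly more censoring.

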### *Pharmacokinetic Analyses*

PK parameters of TTI-621 will be calculated from concentration-time data using noncompartmental analyses. Parameters may include, as appropriate, AUC0- $\tau$ , AUC0- $\infty$ , Cmax, Tmax, t1/2, clearance, and volume of distribution. Results will be reported using conventional summary statistics. The relationship between TTI-621 exposure and various safety indices will be assessed. All final PK analyses will be defined in the final PK analysis plan and/or final Statistical Analysis Plan (SAP) as appropriate.

*Efficacy Analyses*

Efficacy analyses will be conducted using the Full Analysis Set and, where appropriate, the Per-protocol Set; in addition, the ORR will also be presented for the Response-Evaluable Set and will be estimated for each cohort evaluated in the expansion phase using disease-specific response criteria. The DOR will be calculated for a subject who achieves response, and is defined as the number of weeks from the start date of the response (and subsequently confirmed) to the first date recurrent or progressive disease is documented; subjects who are ongoing at the time of the analysis will have the last study visit date included as a censored value for the Kaplan-Meier analysis. If a subject dies, irrespective of cause, without documentation of recurrent or progressive disease beforehand, then the date of death will be used to denote the response end date. PFS is defined as the number of weeks from the date of the first dose of study drug to the earliest of documented recurrent or progressive disease or death due to any cause without prior progression. DOR and PFS will be summarized descriptively using the Kaplan-Meier method with 95% CI calculated using Greenwood's formula. Median follow-up for each endpoint will be estimated according to the Kaplan-Meier estimate of potential follow-up. The PFS rate at selected landmarks (e.g., 6 months) and corresponding 95% CIs will be estimated using the Kaplan-Meier method. Greenwood's formula will be used to calculate the standard errors of the Kaplan-Meier estimate and upper and lower limits of the 95% CI.

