Secondary objectives include characterization of the PK, PD, immunogenicity, and preliminary evidence of antitumor activity of TTI-621 in subjects with relapsed and/or refractory CTCL at higher dose levels of TTI-621.

Secondary endpoints are:

- PK profile, PD, ADA
- Overall response rate and duration of response
- CTCL: organ system overall response rate

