#### **3.7.1 Overall Response Rate**

For each subject, a disease-specific overall assessment will be made by the investigator. The table below indicates the responder and non-responder CRF categories for each type of malignancy.

Type of Hematologic Malignancy	CRF	CRF variable label	CRF Assessment Categories (* indicates responder category, ** indicates progressive disease category)
Lymphoma (Hodgkin or Non-Hodgkin)	Response Assessment – Cheson Lugano Classification 2014	"Overall Visit Response at This Assessment"	CR*, PR*, SD, PD**, NE

Multiple Myeloma	Response Assessment – IMWG	"Overall Objective Response at this assessment"	CR*, sCR*, VGPR*, PR*, SD, PD**, Clinical Relapse**, NE, NA
Acute Myeloid Leukemia	AML Response Assessment – Cheson 2003	"Overall Objective Response at This Assessment"	Morphologic leukemia-free state*, Morphologic complete remission*, Cytogenetic complete remission*, Molecular complete remission*, Partial Remission*, Treatment Failure, Unknown
Chronic Lymphocytic Leukemia	Response Assessment – Hallek 2008	"Overall Visit Response at This Assessment"	Complete Response or Complete Remission*, Complete Response or Complete Remission with Incomplete Marrow Recovery*, Partial Response*, Relapse or Progressive Disease**, Stable Disease, Unknown
Myelodysplastic Syndrome (RAEB-1 or RAEB-2)	Response Assessment – MDS	"Overall Objective Response at this assessment"	CR: Marrow*, CR*, PR*, SD, PD**, NE, NA

A subject will be considered to be a responder if the subject had at least two consecutive assessments at which the subject is identified as a responder according to the table above. A subject will be considered to have progressive disease if the subject had at least one assessment at which the subject is identified as having progressive disease according to the table above. The earliest of the consecutive dates at which a responder assessment is made will be the Date of Response. The earliest date at which a progressive disease assessment is made will be the Date of Progression.

In the full analysis set and the response evaluable set, the Overall Response Rate (ORR) is defined as follows.

$$ORR = 100 * \frac{\text{Number of responders}}{\text{Total number of subjects}}$$

(Note that subjects having a response of NE, NA, Unknown, or missing are included in the denominator in this calculation and summarized as non-responders.)

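### SAP 3.7.2 censors a responder's death in the duration-of-response analysis, whereas the protocol counts it as the end of the response; other rules equal, this can only raise the DOR curve

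*SAP*

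**What the plan says.** **Protocol.** Under Efficacy Analyses, the Synopsis separates two kinds of responder without documented progression. For those alive and still followed, "subjects who are ongoing at the time of the analysis will have the last study visit date included as a censored value". For those who have died, the rule begins "If a subject dies, irrespective of cause, without documentation of recurrent or progressive disease beforehand" and makes the date of death the end of the response. Section 8.4.6 repeats it: "then the date of death will be used to denote the response end date". The list of right-censored subjects in 8.4.6 includes a death only when it follows two or more consecutive missed disease assessments. It also censors subjects who start new anticancer therapy before documented progression.

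**SAP 3.7.2.** The section defines a date of death ("Date of death from any cause as recorded on Death Page CRF"). It uses that date in the PFS formula, which takes the minimum of the progression and death dates. The DOR formula takes a minimum over one date, progression. The censoring table, introduced by the words "In the case of missing dates (ie, subjects without an event", has a row that applies to DOR alone, "Death prior to progression", with the date of death marked as the censoring date.

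**Status of the endpoint.** DOR is a secondary endpoint for Parts 2 and 3 (SAP 1.1.2) and for Part 4 (SAP 1.1.3, "Overall response rate and duration of response").

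**The concern.** The two documents treat the same death in opposite ways. In the SAP, formula and table agree with each other, so this is not a single slip that the other corrects. One responder can be a PFS event and a DOR censoring on the same day.

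Censoring at death treats the response as if it could have continued. The reported curve then no longer estimates the protocol's endpoint, in which a response ends at progression or death. With few responders per cohort, a single recoded death can move the reported median, and the recoding itself can only push it upward.

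**Working it through.** The documents print no DOR figure, so there is nothing to reproduce. The checks are the direction of the effect and its size in small exact cases.

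**Direction.** The Kaplan-Meier estimate is S(t) = product of (1 − d/n) over end times up to t, where n is the number at risk and d the number of events. A responder who dies at time u is in the risk set up to u and out of it afterwards under both rules. Only d at u changes, from 1 (protocol) to 0 (SAP). With no tie at u and n > 1, the SAP curve from u onward is the protocol curve multiplied by n/(n − 1), until the curve reaches zero. It is never lower, provided that all other dates and rules are equal. A numerical check on 100,000 random datasets of 1 to 15 responders, with ties, found none in which the SAP curve or median was lower.

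**Seven responders.** Seven is the smallest number that passes the final Part 3 rule, which rejects at six or fewer of 35 (Protocol 8.3). Assume that all seven ends are observed at different times and that exactly one is a death. Under the protocol, S at the 4th end is 3/7 = 0.429, so the median is the 4th end time. A death at rank r has n = 8 − r at risk:

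| Rank of the death | SAP value of S at 4th end | SAP median |
|---|---|---|
| 1 | 7/6 × 3/7 = 0.500 | midway between 4th and 5th ends |
| 2 | 6/5 × 3/7 = 0.514 | 5th end |
| 3 | 5/4 × 3/7 = 0.536 | 5th end |
| 4 | 4/3 × 3/7 = 0.571 | 5th end |
| 5, 6 or 7 | 3/7 = 0.429 | 4th end, unchanged |

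For ranks 1 to 4 the 5th end multiplies S by 2/3, giving 0.333, 0.343, 0.357 and 0.381. All are below 0.50.

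**Four responders.** Four is 33% of 12, the Part 4 example in SAP 1.2.5. The protocol curve is 0.75, 0.50, 0.25, 0, and the median lies midway between the 2nd and 3rd ends. Under the SAP:
- Death ranked 1st: S = 2/3 at the 2nd end and 1/3 at the 3rd, so the median is the 3rd end.
- Death ranked 2nd: S = 3/4 up to the 3rd end and then 3/8, so the median is the 3rd end.
- Death ranked 3rd: S stays at 0.50 from the 2nd to the 4th end, so the median is midway between those two.
- Death ranked 4th: the median is unchanged.

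Both examples take the midpoint when the curve sits exactly at 0.50. If the first time at or below 0.50 is reported instead, the median does not move for rank 1 of seven or rank 3 of four. The curve is still higher.

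**When the effect is zero.** There is no effect if no responder dies without documented progression. Nor is there any if such deaths occur only after new anticancer therapy or after two or more consecutive missed assessments, because the protocol censors those too (given the same censoring date).

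**The case against.** **The SAP may refine the protocol.** Protocol section 8 leaves final analytical detail to the SAP, and 8.4.6 leaves dating conventions to it for the subjects on its own censoring list. A responder's death without progression is not on that list unless assessments were missed or new therapy was started. Neither clause lets the SAP turn a stated end of response into a censoring.

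**The change may have been deliberate.** The SAP version history attributes version 2.0 partly to notes-to-file and sponsor recommendations that are not available here. This stands as a limit: one can say only that nothing in the protocol or SAP declares or explains the change.

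**The protocol never calls the death an event for DOR.** This is true of the word. But the Synopsis sets such deaths against the subjects whose dates are censored, which leaves little room for another reading.

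**The SAP's DOR need not be higher overall.** A reader might infer that it is always at or above the protocol's. The documents do not support that, because they also date ongoing responders differently: last study visit in the Synopsis; in the SAP, the earlier of last non-progression assessment and start of anticancer treatment. Suppose A dies at week 10, B progresses at week 42, and C is ongoing with a last assessment at week 40 and a last visit at week 50. The Synopsis rules give S(42) = 2/3 × 1/2 = 0.33. The SAP rules give 0, since only B is at risk at week 42. The direction therefore holds for the death rule with other rules equal, and not for the two analyses as whole packages.

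**The consequences are limited.** This stands. DOR is descriptive, and it and the dates of death are both listed (SAP 3.7.2 and 3.5.2), so a reader with the listings could rebuild the protocol's version.

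**Conclusion.** The contradiction is real and should be resolved before DOR is reported. With all other censoring rules equal, the SAP's death rule gives a DOR curve that is never below the protocol's and is higher from each affected death until the curve reaches zero. In the exact examples one early death is enough to raise the median: among the first four of seven ends, or the first three of four, using the midpoint convention.

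Those examples assume one death, distinct end times and no other censoring. The size in this trial cannot be known, because the documents give no number of responders and no number of such deaths.

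Two stronger readings are not supported. A reader might infer a fixed percentage inflation of the median from an assumed share of deaths under constant hazards. That share is not in the documents, and a constant hazard from the response date does not fit SAP 3.7.1, which requires "at least two consecutive assessments at which the subject is identified as a responder", so a counted response cannot end before its confirmation. A reader might also infer that a go/no-go decision is affected. It is not: the Simon rules count responders, and DOR carries no test.

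**What to change.** In SAP 3.7.2:
- Define DOR = [min(date of progression, date of death) − date of response + 1]/7.
- Delete the DOR-only row that censors death before progression.
- State that the remaining rows override the formula, with the content of Protocol 8.4.6: new anticancer therapy, and death or progression after two or more consecutively missed scheduled assessments. The statement is needed because the table presents itself as covering only subjects without an event. Also, a responder who dies after missed assessments now fits two DOR rows with different censoring dates, and the SAP does not say which governs.

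If censoring deaths was intended, declare it as a change from the protocol, give the reason, and also report the protocol-defined DOR.

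The cost is a few lines of SAP text and minor programming, since the date of death is already defined in the same section. The downside is that reported DOR may be somewhat less favourable. The data source for new anticancer therapy and the treatment of non-evaluable assessments in the missed-assessment row are separate points and do not need to be settled here.
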